6.1.6 Follow-up period

Following the last dose of IMP (either as scheduled or prematurely), a post treatment follow-up should be scheduled for all patients 4 weeks (\pm 3 days) after permanent IMP discontinuation.

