10.1.3 Double-blind extension period

Upon completion of the double-blind core treatment period, patients will remain on the same blinded treatment throughout a 53-week double-blind extension period for a total treatment duration of 79 weeks.

The double-blind extension period will consist of 4 visits, occurring at Week 39 (Visit 10), Week 52 (Visit 11), Week 65 (Visit 12), and an end-of-treatment visit at Week 79 (Visit 13).

In the event of abnormal urinalysis findings suspicious of urinary tract infection, urine culture should be performed. Positive urine culture determination will be based upon the criteria of the reporting laboratory.

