10.4.2 General guidelines for reporting adverse events

- All AEs, regardless of seriousness or relationship to IMP/NIMP, spanning from the signature of the ICF until the end of the study as defined by the protocol for that patient, are to be recorded on the corresponding page(s) or screen(s) of the e-CRF.
- Whenever possible, diagnosis or single syndrome should be reported instead of symptoms. The Investigator should specify the date of onset, intensity, action taken with respect to IMP, corrective treatment/therapy given, additional investigations performed, outcome, and his/her opinion as to whether there is a reasonable possibility that the AE was caused by the IMP or by the study procedure(s).
- In this study, the use of concomitant medications including antidiabetic medications may make it difficult to assess the causal relationship, particularly for hypoglycemia. Global Safety Officer with input from other appropriate study team members will determine the causal relationship when it is not clearly provided by the Investigator.
- The Investigator should take appropriate measures to follow all AEs until clinical recovery is complete and laboratory results have returned to normal, or until progression has been stabilized, or until death, in order to ensure the safety of the patients. This may imply that observations will continue beyond the last planned visit per protocol, and that additional investigations may be requested by the monitoring team up to as noticed by the Sponsor.
- When treatment is prematurely discontinued, the patient's observations will continue until the end of the study as defined by the protocol for that patient.
- Laboratory, vital signs or ECG abnormalities are to be recorded as AEs if they are medically relevant based on the Investigator's medical judgement, eg.:
 - Symptomatic and/or
 - Requiring either corrective treatment or consultation, and/or
 - Leading to IMP discontinuation or modification of dosing, and/or
 - Fulfilling a seriousness criterion, and/or
 - Defined as an AESI or EOSI.

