2.1.4 Safety endpoints

The safety analysis will be based on the reported adverse events (AEs), hypoglycemia, and other safety information, such as clinical laboratory data, vital signs, electrocardiogram (ECG), and physical examination, etc.

Observation period

The observation period will be divided into 4 epochs:

- The **screening** epoch is defined as the time from the signed informed consent date up to the first administration of the double-blind IMP.
- The treatment epoch is defined as the time from the first administration of double-blind IMP to the last administration of double-blind IMP. This epoch includes the 26-week double-blind core treatment period and the 53-week double-blind extension treatment period. The 26-week double-blind core treatment period is the time from the first administration of double-blind IMP to the last administration of double-blind IMP on or before Visit 9/Week 26 (or Day 182 if Visit 9/Week 26 date is missing).
- The **residual treatment** epoch is defined as the time from the last administration of double-blind IMP to the last administration of double-blind IMP + 10 days (1 day for hypoglycemia).

The treatment-emergent adverse event (TEAE) period for the 79-week double-blind entire treatment period will include both **treatment** and **residual treatment** epochs (See the TEAE period for the 26-week double-blind core treatment period in [Section 2.5.4](#)).

- The **posttreatment** epoch is defined as the period of time starting the day after the end of the treatment-emergent adverse event period up to the last protocol-planned visit or the resolution/stabilization of all serious adverse events (SAE), adverse events of special interest (AESI) and events of special interest (EOSI), whichever is later.

The on-study observation period is defined as the time from start of double-blind treatment until the end of the study (defined as the last scheduled visit for those who completed the study and the date collected on e-CRF page “Completion of End of Study/Follow-up” for those who did not complete the study).

The post-study observation period is defined as the time from the day after the end of the study until the resolution/stabilization of all SAE, AESI and EOSI if applicable.

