2.4.5.2 Analyses of AEs

Generalities

The primary focus of AE reporting will be on treatment-emergent AEs. Pretreatment and posttreatment AEs will be described separately.

If an AE date/time of onset (occurrence, worsening, or becoming serious) is incomplete, an imputation algorithm will be used to classify the AE as pretreatment, treatment-emergent, or posttreatment. The algorithm for imputing date/time of onset will be conservative and will classify an AE as treatment emergent unless there is definitive information to determine it is pretreatment or posttreatment. Details on classification of AEs with missing or partial onset dates are provided in [Section 2.5.3](#).

Adverse event incidence tables will be presented by SOC, HLGT, HLT, and PT, sorted by the internationally agreed order for SOCs and alphabetic order for HLGT, HLT and PT within a SOC, the number (n) and percentage (%) of patients experiencing an adverse event. Multiple occurrences of the same event by PT in the same patient will be counted only once in the tables within a treatment phase. The denominator for computation of percentages is the safety population within each treatment group.

Sorting within tables ensures the same presentation for the set of all adverse events within the observation period (pretreatment, treatment-emergent, and posttreatment). For that purpose, the table of all treatment-emergent adverse events presented by primary SOC and PT sorted by the internationally agreed SOC order and decreasing frequency of PTs within SOCs in the sotagliflozin group will define the presentation order for all other similar tables unless otherwise specified. In case of equal frequency regarding PTs, alphabetical order will be used.

Analysis of all treatment-emergent AEs

The following treatment-emergent AE summaries will be generated during the 26-week core and the 79-week entire treatment periods respectively in the safety population.

- Overview of treatment-emergent AEs, summarizing number (%) of patients with any
 - Treatment-emergent AE
 - Serious treatment-emergent AE
 - Treatment-emergent AE leading to death
 - Treatment-emergent AE leading to permanent treatment discontinuation.
- All treatment-emergent AEs by primary SOC, showing number (%) of patients with at least 1 treatment-emergent AE, sorted by internationally agreed order of primary SOC.

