- ii. recorded in eCRF “Renal Event – Dialysis”,
- iii. identified as “Renal transplant” in eCRF “Other procedure”,

Renal death will be part of all deaths specified above.

Other EOSIs

For EOSIs that are not adjudicated, the number (%) of patients with at least one event will be summarized by treatment group and by PT (as identified in [Table 3](#) in [Section 2.1.4.2](#)).

Severe hypoglycemia will be included in the summary of hypoglycemia (See [Section 2.4.5.1](#)).

AE leading to an amputation is described in the section below.

Analysis of Amputation

The number (%) of patients with amputation will be summarized by treatment group and by PT and LLT during the study (ie, regardless of on- or post-treatment). Amputation is a procedure recorded in eCRF form “Other Procedures related to Amputation”. Patients who had a procedure related to amputation will be listed.

The number (%) of patients with an “AE leading to an amputation” will be summarized by treatment group and by PT. The “AE leading to an amputation” is determined by the AE identifier recorded in eCRF “Other Procedures related to Amputation” when “AE correction” is chosen as the reason for the amputation procedure.

In addition, the number (%) of patients with an “AE potentially leading to an amputation” will be summarized by treatment group and by PT (as identified in [Table 3 in Section 2.1.4.2](#)). These PTs in [Table 3](#) were requested by the European Medicines Agency (EMA)/ Pharmacovigilance Risk Assessment Committee (PRAC) Assessment Report, 9 February 2017). The associated list will be provided as well, with patients who had an amputation procedure flagged. “AE potentially leading to an amputation” represents the condition that may potentially lead to the amputation procedure, but not in all cases an amputation has occurred.

Analysis of pretreatment and posttreatment AEs

- All pretreatment AEs by primary SOC and PT, showing the number (%) of patients with at least 1 pretreatment AE, sorted by the internationally agreed SOC order and decreasing incidence of PTs within each SOC in the sotagliflozin group
- All posttreatment AEs by primary SOC and PT, showing the number (%) of patients with at least 1 posttreatment AE, sorted by the internationally agreed SOC order and decreasing incidence of PTs within each SOC in the sotagliflozin group.

Listings

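### Post-treatment AE percentages mix AE risk with very unequal follow-up, so differing early discontinuation between arms can alone create or hide a difference

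*SAP*

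**What the plan says.** SAP 2.4.5.2 lists, under pretreatment and posttreatment AEs, "All posttreatment AEs by primary SOC and PT, showing the number (%) of patients with at least 1 posttreatment AE". The general rule in the same section is "The denominator for computation of percentages is the safety population within each treatment group".

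SAP 2.1.4 ends the treatment-emergent period 10 days after the last dose (1 day for hypoglycemia). It defines the post-treatment epoch as "the period of time starting the day after the end of the treatment-emergent adverse event period up to the last protocol-planned visit", or until SAEs, AESIs and EOSIs have resolved or stabilized if that is later.

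Protocol 10.1.3 keeps patients on blinded drug "for a total treatment duration of 79 weeks". Protocol 6.1.6 says "a post treatment follow-up should be scheduled for all patients 4 weeks" (±3 days) after permanent discontinuation. For patients who stop early, Protocol 10.4.2 says that "observations will continue until the end of the study as defined by the protocol for that patient", and SAP 1.1 expects them to remain in the study.

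SAP 2.4.5.1 specifies rates per 100 patient-years for hypoglycemia. Nothing equivalent is given for post-treatment AEs.

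**The concern.** A percentage of patients with at least one event is comparable between arms only if the arms are observed for similar lengths of time. Here the time at risk depends on when the patient stopped drug: a few weeks for completers, potentially more than a year for early stoppers. Whether and when a patient stops may itself be affected by treatment.

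This is the only general by-arm AE summary for the off-drug period. AESI and EOSI summaries are confined to the 79-week treatment period; only deaths and amputations are summarized beyond it. Protocol 8.9 asks for monitoring of blood pressure increases after withdrawal, so an off-drug effect is something a reader may look for in this table. SAP 2.4.5 also allows relative risks against placebo where relevant, and these would inherit the problem.

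**Working it through.** **Inputs from the documents.** Visit 13 is Day 551 and Visit 14 is Day 579 (flow chart); the follow-up visit is 28 ± 3 days after the last dose; the residual period is 10 days; there are 250 patients per arm. Schedule check: 551 + 28 = 579, which reproduces the Visit 14 day. (The heading of Protocol 10.1.4.1 says Week 82; the flow chart's Week 83, the 4-week interval and the 87-week total all support Day 579.)

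**Post-treatment days per patient.**
- Completer: 579 − (551 + 10) = 18, or 15 to 21 with the visit window.
- Early stopper on day *d*, followed to Day 551: 551 − *d* − 10. Day 1 gives 540, Day 84 gives 457 (457/18 = 25 times a completer), Day 182 gives 359, Day 365 gives 176.

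**Assumptions, none of them in the documents.** Constant AE rate λ, equal in both arms, of 0.5, 1 or 2 per patient-year; stop days uniform over Days 1 to 551; stopper time max(541 − *d*, 18), mean 266 days. A stopper who is not retained leaves after the 4-week visit and contributes 18 days.

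**Formulas.** For one patient, P(at least 1 AE) = 1 − exp(−λ × days/365.25). Averaged over stop days this is 2.4%, 4.8% and 9.4% for a completer, and 28.9%, 47.1% and 67.0% for a fully followed stopper, at λ = 0.5, 1 and 2. With a proportion *q* stopping and a share *r* of them retained, the arm percentage is *q*[*r*·P(stopper) + (1 − *r*)·P(completer)] + (1 − *q*)·P(completer).

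| Retained | λ | 10% stop | 15% stop | 20% stop | Ratio 15/10 | Ratio 20/10 |
|---|---|---|---|---|---|---|
| All | 0.5 | 5.1% | 6.4% | 7.7% | 1.26 | 1.52 |
| All | 1 | 9.0% | 11.1% | 13.3% | 1.23 | 1.47 |
| All | 2 | 15.1% | 18.0% | 20.9% | 1.19 | 1.38 |
| Half | 0.5 | 3.8% | 4.4% | 5.1% | 1.18 | 1.35 |
| Half | 1 | 6.9% | 8.0% | 9.0% | 1.15 | 1.31 |
| Half | 2 | 12.3% | 13.7% | 15.1% | 1.12 | 1.23 |

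Every ratio should be 1.00, because the AE rate is the same in both arms. Spreading stop days over Days 1 to 512 instead gives 1.40 to 1.54 (all retained) and 1.25 to 1.37 (half retained) for 20% against 10%.

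**Timing alone.** With 15% stopping in both arms and full retention, but by Day 182 in one arm and after Day 365 in the other (a deliberate extreme), λ = 1 gives 14.7% against 7.1%, a ratio of 2.07.

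**Person-time.** At 10% stopping with full retention, stoppers supply 0.10 × 265.7 / (0.10 × 265.7 + 0.90 × 18) = 62% of post-treatment time.

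**The case against.** The strongest reply is that little depends on this table. The SAP puts the focus on treatment-emergent AEs and describes post-treatment AEs separately, with no safety testing. Discontinuation is shown by arm and in Kaplan-Meier plots, so an imbalance would be visible, and the listings carry onset and discontinuation dates. Deaths and amputations are summarized independently of this table. Even the larger artefact is noisy: at λ = 1 with full retention, 10% against 20% stopping is about 23 against 33 patients, ratio 1.47 with a 95% CI of roughly 0.9 to 2.4, before any split by SOC and PT. All of this stands, and it sets the severity. It does not remove the defect, because nobody can recover person-time by SOC and PT from a discontinuation curve.

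Retention is also uncertain. The protocol promises every effort, accepts telephone contact in place of visits and lets patients withdraw. That too stands, and is why the half-retained rows are shown.

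A reader might infer that the table mainly compares how many patients stopped early. The documents do not support that: they state no discontinuation rate, retention or arm difference. With stop days over Days 1 to 512, 5% to 30% stopping and half or full retention, early stoppers make up anywhere from 18% to 84% of the patients counted. Nor is it right that the percentage is unrelated to risk after stopping. With 10% stopping and full retention, raising the AE rate from 0.5 to 2 per patient-year moves it from 5.1% to 15.1%. Risk is in the figure, but mixed with follow-up time.

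**Conclusion.** The point holds as a limited reporting defect. The unequal observation time and the whole-arm denominator come directly from the documents; the 18-day and 540-day figures are planned observation, and either can lengthen while SAEs, AESIs or EOSIs are followed to resolution. The size of any distortion is not known. Under the stated assumptions the spurious ratio is 1.12 to 1.26 for 10% against 15% stopping and 1.23 to 1.52 for 10% against 20%, across both retention scenarios. It vanishes if the number, timing and retention of stops are the same in both arms; equal numbers alone are not enough. Nothing here touches the treatment-emergent AE tables or any efficacy analysis. Worth correcting, low severity.

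**What to change.** In SAP 2.4.5.2, do one or both of the following.

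1. Add, by arm, patients with events and events per 100 patient-years of post-treatment observation. Define that time from day 11 after the last dose to the last planned visit or study exit. For the patient-based rate, stop the clock at the first event. Dividing patients with events by total time would leave a smaller bias the other way: in the λ = 1, full-retention example, 22.6/29.3 = 0.77 against 33.2/46.2 = 0.72 per patient-year, although the true rates are equal.
2. Limit the by-arm n (%) table to days 11 to 25 after the last dose, with patients still under observation on day 11 as denominator, and put later off-drug AEs in a separate patient-year table. Day 25 is the earliest end of the 4-week visit window. Ending at day 31 looks natural but is not shared: completers may be last seen from day 25, while retained stoppers are observed throughout.

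The common window also protects against an AE rate that changes with time since stopping, which a single patient-year rate does not.

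Cost: SAP wording and one extra table, with no new data. The common-window table will contain fewer events, and the rest move to the second table.

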2.4.5.3 Deaths

The following summaries of deaths will be generated.

- Number (%) of patients who died by study period (on-study, on-treatment, post-study)
- Deaths in nonrandomized patients or randomized but not treated patients
- Treatment-emergent AEs leading to death (death as an outcome on the adverse event case report form page as reported by the Investigator) by primary SOC, HLT, HLT, and PT showing number (%) of patients sorted by internationally agreed SOC order, with HLT, HLT, and PT presented in alphabetical order within each SOC.

2.4.5.4 Analyses of laboratory variables

Laboratory parameters will be grouped and summarized by biological function as described in [Section 2.1.4.4](#).

The summary statistics (including number, mean, median, Q1, Q3, standard deviation, minimum and maximum) of all laboratory variables (central laboratory values, changes from baseline) will be calculated for each applicable visit or study assessment (screening, baseline, postbaseline time points, last on-treatment value) by treatment group during the entire treatment period only.

The incidence of PCSAs (list provided in Appendix E) at any time during the treatment-emergent adverse event period will be summarized for each laboratory test by biological function and treatment group whatever the baseline level and/or according to the following baseline status categories:

- Normal/missing
- Abnormal according to PCSA criterion or criteria.

For parameters for which no PCSA criteria are defined, similar table(s) using the normal range will be provided.

All measurements collected during the treatment-emergent AE period, including values from unscheduled visits, will be considered for the PCSA summaries. These summaries will include patients in the safety population who have at least 1 assessment performed during the treatment-emergent AE period. When a PCSA definition involves a Change from Baseline value, patients must also have a baseline value to be included in the summaries, and when required by the definition of the abnormality, patients must also have available laboratory normal ranges.

A listing of patients with at least 1 post-baseline PCSA (or out of normal range when no PCSA criterion is defined) will be provided and will display the entire patients' profile across time for all parameters belonging to the corresponding biological function. Individual data listings will include flags when applicable:

- Baseline values will be flagged "B".
- Normal laboratory ranges, available for most laboratory parameters, will be identified as ULN and LLN. Baseline, last on-treatment value, and individual data will be flagged "L" if the value is below the LLN and will be flagged "H" if it is above the ULN.
- Laboratory PCSA criteria will be used for the corresponding laboratory parameters. Values reaching a PCSA limit will be flagged (+, ++, -, or -- depending upon the direction and level of the abnormality). Flags for WBC and differential counts will be determined using data expressed in international units.

For parameters whose PCSA criteria are multiples of the ULN, the parameter's value will also be expressed as a multiple of the ULN in the individual data provided.

Drug-induced liver injury

The liver function tests, namely AST, ALT, alkaline phosphatase, and total bilirubin, are used to assess possible drug-induced liver toxicity. The proportion of patients with PCSA values at any post-baseline visit by baseline status will be displayed by treatment group for each parameter. The proportion of patients with PCSA values at any post-baseline visit will also be displayed by duration of exposure for each treatment group (only if a tabulation summary is necessary).

Listing of possible Hy's law cases identified by treatment group (eg, patients with any elevated ALT>3 x ULN, and associated with an increase in bilirubin ≥ 2 x ULN) with ALT, AST, alkaline phosphatase, total bilirubin, and the following complementary parameters (if available): conjugated bilirubin and prothrombin time/international normalized ratio, creatine phosphokinase, serum creatinine, complete blood count, anti-HAV IgM, anti-HBc IgM, anti-HCV and HCV RNA, anti-CMV IgM and anti-HEV IgM antibodies, auto-antibodies: anti-nuclear, anti-DNA, anti-smooth muscle, Epstein-Barr virus, herpes viruses, and anti-LKM.

2.4.5.5 Analyses of vital sign variables

The summary statistics (including number, mean, median, Q1, Q3, standard deviation, minimum and maximum) of heart rate, temperature and respiratory rate (observed values or mean of observed values, and changes from baseline) will be calculated for each applicable visit or study assessment (baseline, post-baseline time points, last on-treatment value) by treatment group during the entire treatment period only.

The incidence of PCSAs at any time during the treatment-emergent adverse event period will be summarized by treatment group for SBP, DBP and HR. All measurements collected during the treatment-emergent AE periods, including values from unscheduled visits, will be considered for the PCSA summaries. The summaries will include patients in the safety population who have at least 1 assessment performed during the treatment-emergent AE period. When a PCSA definition involves a Change from Baseline value, patients must also have a baseline value to be included in the summaries.

A listing of patients with at least 1 post-baseline PCSA will be provided and will display the patient's profile over time of all vital sign parameters. Individual data listings will include the following flags:

- Baseline values will be flagged "B",
- Parameter values reaching a PCSA limit will be flagged (+, or - depending of the direction).

2.4.5.6 Analyses of electrocardiogram variables

Shift tables will be provided to present ECG status according to baseline status (Normal/Missing, Abnormal) for each treatment group during the treatment-emergent AE period. Supportive listings of patients with abnormal ECG status at any post-baseline visit will be provided.

